4.7.3 Physical Examination, Vital Signs, and Electrocardiogram Findings

The number and percentage of subjects with normal, abnormal and clinical significant, abnormal but not clinically significant physical exam findings will be summarized by visit and dose.

Vital sign measurements and change from baseline will be summarized at each scheduled time point by cohort using descriptive statistics. Baseline is defined as the Day 0 (pre-dose) measurement. If the baseline measurement is missing, the last measurement prior to the first study drug administration.

Arithmetic mean of parameters from triplicate ECG will be calculated first for each subject at each planned time point. Then summary statistics of ECG test parameters (mean of triplicate) and change from baseline to each post-dose time point will be calculated. Shift tables for ECG test result category change (normal, abnormal not clinically significant, abnormal clinically significant) from baseline to each post-baseline time point showing number and percentage of subjects with movement between categories will be presented by treatment group. The worst overall interpretation at each visit from the three triplicate readings are summarized.

The number and percentage of subjects with elevated QTcF during the post baseline period will be presented for the following categories: QTcF worsening to >450 msec, >480 msec, and >500 msec from baseline, and increase in QTcF from baseline >30 msec and >60 msec.

Actual sampling times that are outside the scheduled sampling times window described in [Table 5](#) will be excluded from summary statistics.

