3.1.4 Vital Sign Measurements

Vital sign assessments will include measurements of sitting blood pressure (mm Hg), heart rate (beats per minute), respiration rate (breaths per minute), pulse oximetry, and oral temperature (Celsius). Abnormal results are to be repeated after 5 minutes of rest. See [Table 4](#) for timing window allowances with respect to measurement collection.

When vital signs are to be collected at the same time point as a blood collection, vital signs should be collected first. Vital sign measurements will be collected after the subject has been sitting for 5 minutes. Subjects should be seated quietly for at least 5 minutes in a chair with their backs supported, their feet flat on the floor (legs uncrossed), and their arms bared on a

hard surface, with the arm slightly abducted and bent, with palm up and the midpoint of upper arm at heart level. Correct cuff and bladder size should be utilized and the same cuff and arm should be used per subject throughout study.

Vital sign measurements are to be obtained immediately prior to the infusion; 15, 30, and 45 minutes after the start of the infusion; at completion of the infusion; 30 minutes, 1 hour, and 2 hours following completion of the infusion. Abnormalities in vital sign measurements will be graded in severity per the National Cancer Institute Common Terminology Criteria for Adverse Events (NCI CTCAE) scale Version 4.03.

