4.7 Safety Analyses

All statistical analysis of safety outcomes will be descriptive. Safety observations and measurements include AEs, treatment-emergent AEs (TEAEs), SAEs, clinical safety laboratory tests, vital sign measurements, physical examinations, and ECGs. The incidence of AEs, TEAEs and SAEs will be summarized by cohort, severity and relationship to study product. Baseline for safety parameters is defined as Day 0 (pre-dose) measurement. If missing, the last measurement prior to the first study drug administration will be used as the baseline value.

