- b. Vital sign measurements (sitting blood pressure, heart rate, respiratory rate, and oral temperature) to be obtained after 5 minutes of seated rest. Any abnormal measurements are to be repeated after 5 minutes of rest. On Days 0, 7, 14, 21, and 28, vital sign measurements will be collected immediately prior to the infusion; 15, 30, and 45 minutes after the start of the infusion; at completion of the infusion; and 30 minutes, 1 hour, and 2 hours following completion of the infusion.
- c. Pulse oximetry: On Days 0, 7, 14, 21, and 28, pulse oximetry to be measured immediately prior to the infusion; 15, 30, and 45 minutes after the start of the infusion; at completion of the infusion; and 30 minutes, 1 hour and 2 hours following completion of the infusion.
- d. Clinical safety labs: hematology, clinical chemistry, and urinalysis (See Protocol Section 7.5 for a complete list). Full clinical safety laboratory draws will be collected at screening and on Days 0, 7, 14, 21, 28, 33, 42, 56, 84, and 112.
- e. Pregnancy test (women of childbearing potential only): To be performed at time of screening, prior to first dose of SYNT001 on Day 0, and on Days 56 and 112. Urine or serum test is acceptable; however, positive urine tests must be confirmed with serum testing.
- f. Digital 12-lead ECG to be obtained in triplicate at least 1 to 2 minutes apart and after 5 minutes of rest in a supine position. See Protocol Section 7.6 for additional information. On Days 0 and 28 to be obtained 5 minutes after the completion of infusion. Day 12 ECG will be collected only if the visit is conducted at the study site.
- g. Serology: Testing at Day 56 will not be done for any subject whose baseline titer is below the level of detection. If the Day 56 results are greater than 30% below the baseline value, or if the subject falls below the level of detection, the subject will be re-tested at Day 84; if still below the baseline value (or level of detection), the subject will be re-tested at Day 112. Any subject whose baseline value for tetanus or VZV was above the detectable level at baseline, and is not within 30% of the baseline value or is below the detectable level by Day 112, will be referred to their primary care physician for further management. See Protocol Section 7.5.3 for additional information.

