Inclusion/exclusion	X											
Physical examination ^a	X	X	X	X	X	X	X	X	X	X		X
Vital signs ^b	X	X	X	X	X	X	X	X	X	X	X	X
Pulse oximetry ^c		X	X	X	X	X	X	X	X			
Clinical safety labs ^d	X	X	X	X	X	X	X	X	X	X	X	X
Pregnancy test ^e	X	X			X					X		X
Hepatitis and HIV screen	X											
12-lead ECG ^f	X	X		X	X					X		X
Tetanus and VZV antibodies ^g		X			X					X		X
PDAI ^h	X	X	X	X	X	X	X	X	X	X	X	X
PK sampling ⁱ		X	X	X	X				X			
Immunogenicity ^j	X	X	X	X	X	X	X	X	X	X	X	X
Study drug administration ^k		X	X	X	X	X	X	X	X			
Immunoglobulins (IgG, IgA, IgM) and IgG subtypes (IgG1-4) ^l	X	X	X	X	X	X	X	X	X	X	X	X ^q
CIC		X	X	X	X	X	X	X	X	X	X	X
Anti-Dsg (1 and 3) antibody titers	X	X	X	X	X	X	X	X	X	X	X	X
C3 and AECA ^m	X	X	X	X	X	X	X	X	X	X	X	X
FCGR2A by buccal swab ⁿ		X										
RNA sequencing		X			X					X		
Immunophenotyping ^o		X			X					X		
Exploratory pemphigus immune response biomarkers		X	X	X	X	X	X	X	X	X	X	X
Photography ^p		X	X	X	X	X	X	X	X	X	X	X

HR-QoL assessments		X			X					X		X
Adverse events	To be collected from the date that the ICF is signed through the last study visit											
Concomitant medications	To be collected from within 14 days prior to Day 0 through the last study visit											

Abbreviations: CIC = circulating immune complexes; d = day(s); ECG = electrocardiogram; EOS = end of study; ET= early termination; FcGR2a= Fc gamma R2a receptor; HIV = human immunodeficiency virus; HR-QoL = health-related quality of life; ICF = informed consent form; Ig = immunoglobulin; PDAI = Pemphigus Disease Area Index; PK = pharmacokinetic; VZV = varicella-zoster virus

- a. Complete physical examination, including weight, to be performed. Height and body mass index will be additional assessments conducted at screening only.
- b. Vital sign measurements (sitting blood pressure, heart rate, respiratory rate, and oral temperature) to be obtained after 5 minutes of seated rest. Any abnormal measurements are to be repeated after 5 minutes of rest. Vital sign measurements will be taken on all study visits. On dosing days, vital sign measurements will be collected immediately prior to the infusion; 15, 30, and 45 minutes after the start of the infusion; at completion of the infusion; and 30 minutes, 1 hour and 2 hours following completion of the infusion.

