- l. Immunoglobulins (IgG, IgA, IgM) and IgG subtypes (IgG 1-4): Collected for measurements of IgG, IgG subtypes (IgG1-4), IgA, and IgM at every visit. On dosing days, samples are collected prior to infusion of study drug. See Protocol Section 7.5.5 for additional information.
- m. Exploratory pharmacodynamic samples (C3 and AECA): Collected pre-dose when collected on dosing days. See Protocol Section 7.5.5 for complete information.
- n. Buccal samples to be collected pre-dose.
- o. Immunophenotyping by flow cytometry for measurement of CD3+CD4+ T, CD3+CD8+ T, monocytes, natural killer (NK) cells, and B cells. Collect samples pre-dose on dosing days.
- p. Photographs of all active lesions taken pre-dose on dosing days. Subjects who begin a steroid taper will have additional photographs taken at the clinic visit during which the decision to begin the taper is made.
- q. Subjects whose total IgG is not within 30% of their Day 0 baseline value and not above 500 mg/dL at the Day 140 visit will be referred for further management.

Table 4. Timing Window Allowances for PK/PD Sampling, ECG, and Vital Sign Measurements at Dosing Visits

Time Point	Tolerance Window	
	Cohort 1	Cohort 2
Pharmacokinetic Sampling		
0 hour	-240 minutes to 0 hour	-240 minutes to 0 hour
5 minutes post end-of-infusion	±5 minutes	±5 minutes
1 hour post end-of-infusion	N/A	±15 minutes
2 hour post end-of-infusion	±15 minutes	±15 minutes
4 and 6 hours post end-of-infusion	±15 minutes	N/A
24 hours (1 day) post end-of-infusion	±60 minutes	N/A
48 hours (2 days) post end-of-infusion	±120 minutes	N/A
Pharmacodynamic Sampling		
0 hour	-240 minutes to 0 hour	-240 minutes to 0 hour
24 hours (1 day) post end-of-infusion	±60 minutes	N/A
48 hours (2 days) post end-of-infusion	±120 minutes	N/A
ECG		
5 minutes post end-of-infusion	±10 minutes	±10 minutes
Vital Signs^a		
0 hour	-240 minutes to 0 hour	-240 minutes to 0 hour
15, 30, and 45 minutes after start of infusion	±5 minutes	±5 minutes
At completion of the infusion	±10 minutes	±10 minutes
30 minutes, 1 and 2 hours post end-of-infusion	±10 minutes	±10 minutes

Abbreviations: ECG = electrocardiogram; N/A = not applicable; PD = pharmacodynamics; PK = pharmacokinetic.

a. Vital signs to include blood pressure, pulse rate, respiratory rate, oral temperature, and pulse oximetry.

Table 5. Pharmacodynamic Assessments

Parameter	Collection Time Points	
	Cohort 1	Cohort 2 ^a

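### Vital-sign change is summarised only from Day 0, so at later infusions acute change is mixed with between-visit drift, and vital-sign CTCAE grades have no table of their own

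*SAP*

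**What the plan says.** SAP section 4.7.3 fixes the analysis: "Vital sign measurements and change from baseline will be summarized at each scheduled time point by cohort using descriptive statistics". The same section fixes the reference: "Baseline is defined as the Day 0 (pre-dose) measurement". Section 4.7 gives the same rule for safety data in general: "Baseline for safety parameters is defined as Day 0 (pre-dose) measurement". If that reading is missing, the last one before the first dose replaces it.

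The collection schedule is much denser. Section 3.1.4 states: "Vital sign measurements are to be obtained immediately prior to the infusion; 15, 30, and 45 minutes after the start of the infusion". It then adds readings at completion and at 30 minutes, 1 hour and 2 hours afterwards. Appendix A repeats this for both cohorts: "On Days 0, 7, 14, 21, and 28, vital sign measurements will be collected immediately prior to the infusion" (Table 2, Cohort 1) and "On dosing days, vital sign measurements will be collected immediately prior to the infusion" (Table 3, Cohort 2).

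Section 3.1.4 also requires severity grading: "Abnormalities in vital sign measurements will be graded in severity per the National Cancer Institute Common Terminology Criteria for Adverse Events". Section 4.7.3 names no table for those grades.

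**The concern.** A reading before each infusion and seven from 15 minutes after its start is a schedule suited to detecting acute change. The natural comparison is each reading against the one taken before that same infusion, and the SAP never defines it. From the second infusion on, the planned change also carries whatever has moved since Day 0, such as disease state, corticosteroid dose or ordinary day-to-day variation.

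Vital signs are a component of the primary safety endpoint (section 2.1). Section 3.1.11 names allergic reactions as a possible consequence of anti-drug antibodies, and section 4.5 plans a summary of medication for potential infusion-related reactions. The age of the reference also differs by dose level in Cohort 2. Under the planned regimen the loading infusions fall on Days 0 to 14 and the maintenance infusions on Days 28 to 84, so a comparison of acute change between the two is entangled with time since Day 0.

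The missing grade table leaves a second, smaller gap: an abnormality that is graded but not reported as an adverse event appears in no summary.

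**Working it through.** The SAP states no precision or sample-size figure for vital signs, so there is nothing to reproduce. The check counts the affected readings, separates the two parts of the change, and asks what the planned tables allow a reader to recover.

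**Inputs from the SAP**
- Infusions under the planned regimen (section 3.1): 5 in Cohort 1; 3 + 5 = 8 in Cohort 2.
- Dosing days (Tables 2 and 3): 0, 7, 14, 21, 28 in Cohort 1; 0, 7, 14, 28, 42, 56, 70, 84 in Cohort 2.
- Readings after the start of each infusion (section 3.1.4): 3 during, 1 at completion, 3 afterwards = 7.
- Enrolment caps (section 3.1): 8 and 12 subjects.

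**1. Readings compared with a value from an earlier visit**

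| | Cohort 1 | Cohort 2 |
|---|---|---|
| Infusions affected | 4 of 5 | 7 of 8 |
| Time points affected | 4 × 7 = 28 of 5 × 7 = 35 (80%) | 7 × 7 = 49 of 8 × 7 = 56 (87.5%) |
| Oldest reference | 28 days | 84 days |
| Infusions affected at the cap | 8 × 4 = 32 of 40 | 12 × 7 = 84 of 96 |

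**2. The two parts of the change**

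Let X be a reading during or after an infusion, P that visit's pre-infusion reading, and B the Day 0 pre-dose reading. Then

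X − B = (X − P) + (P − B).

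The first term is the within-visit change and the second is drift since Day 0. At the first infusion P = B and the drift term is zero. As an illustration with assumed values, a subject 10 mmHg above Day 0 before the infusion who then falls 15 mmHg is reported as +10 − 15 = −5 mmHg.

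**3. What the planned summaries give back**
- Mean: mean(X − P) = mean(X) − mean(P). Both are summarised, so the mean within-visit change is recoverable if the same subjects contribute at both times.
- SD: Var(X − P) = Var(X) + Var(P) − 2 Cov(X, P). The tables give the two variances but not the covariance, so the SD is not recoverable from them.
- Minimum and maximum: these cannot be subtracted, because the extremes of X and P may belong to different subjects. The extremes of X − B are shown but include the drift.

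**4. Size of the effect on spread (assumed correlations)**

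With a common SD at all time points, SD(change) = SD × √(2(1 − r)). The ratio of SD for change from Day 0 to SD for same-visit change is therefore √((1 − r_between)/(1 − r_within)). The SAP gives neither correlation. Assuming 0.7 to 0.9 within a visit and 0.4 to 0.7 between visits:

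| r_within | r_between | Ratio |
|---|---|---|
| 0.7 | 0.7 | √(0.3/0.3) = 1.00 |
| 0.8 | 0.5 | √(0.5/0.2) = 1.58 |
| 0.9 | 0.4 | √(0.6/0.1) = 2.45 |

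**5. Grades, set beside the other safety data**
- Laboratory tests (section 4.7.2): incidence of CTCAE grades, shift tables for chemistry and worst on-study grade.
- ECG (section 4.7.3): shift tables and QTcF categories.
- Vital signs (section 4.7.3): descriptive statistics of value and change only.
- Adverse events (section 4.7.1): tabulated by CTCAE grade, so a vital-sign abnormality enters here only if it is reported as an event. Sections 3.1.3, 3.1.5 and 3.1.12 say when physical-examination, laboratory and ECG abnormalities are recorded as events. Section 3.1.4 has no such rule, though the protocol, which is not at hand, may.

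**The case against.** A Day 0 baseline is a usual convention, is applied consistently across the safety sections, and is tied to no test or decision rule. All captured data are listed (sections 4 and 4.1), and section 1 allows additional analyses to be identified in the study report. This stands. It is a reason to keep the Day 0 change and add to it.

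Some stronger readings are tempting but not supported:
- A reader might infer that a fall during a later infusion would be invisible. It would not be. Pre-infusion values are scheduled time points, so the example above would show as +10 and then −5 in successive rows.
- A reader might infer that averaging over 8 or 12 subjects conceals one marked excursion. Section 4.1 includes minimum and maximum, so extremes of value and of change from Day 0 are displayed. What is missing is the extreme of the within-visit change.
- A reader might infer that grades go unreported altogether. Abnormalities reported as adverse events are tabulated by grade.
- A reader might see a conflict between a reading immediately before the infusion and Table 4, whose window runs from minus "240 minutes to 0 hour". Section 3.1.4 itself refers to Table 4 for timing allowances, so this is a nominal time with a tolerance. It matters only as a limit on how recent a same-visit reference will be.

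**Conclusion.** The point holds in a limited form and is minor. After the first infusion, the only planned measure of vital-sign change combines acute effect and between-visit drift, at 4 of 5 infusions in Cohort 1 and 7 of 8 in Cohort 2. These counts assume the planned regimen; Table 1 allows the Cohort 2 schedule to be modified. The mean within-visit change remains recoverable when the same subjects contribute. Its SD, its range and individual within-infusion excursions are in no summary table. Vital-sign grades are tabulated only through adverse-event reporting.

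The gain in precision is uncertain. The ratio of 1.0 to 2.45 rests on assumed correlations and equal variances, and at the lower end there is no gain. The mixing of acute change with drift does not depend on those assumptions. It is therefore too strong to say that infusion effects would be lost or that the Day 0 baseline is an error.

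**What to change.** In section 4.7.3:
- For each reading during or after an infusion, add a descriptive summary of change from that visit's own pre-infusion reading, by cohort, infusion and time point. Keep change from Day 0 for trends between visits.
- Add a table of the number and percentage of subjects by worst vital-sign CTCAE grade, per infusion and cohort.

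The cost is SAP wording, one derived variable and additional tables; no new measurements are needed. The output becomes longer. The same-visit reference may be up to 240 minutes old under the Table 4 tolerance, which a footnote to the new summary should state.

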3.1.11 Immunogenicity Testing

SYNT001 is being developed for the acute and chronic therapy of autoimmune disorders. Although SYNT001 is a humanized IgG4 mAb, exposure to SYNT001 in clinical trials could result in the development of ADAs, with potential consequences ranging from neutralization with possible lessening of drug efficacy to safety consequences such as allergic reactions.

Testing will first detect binding ADAs. Then, for all confirmed positive samples, an ADA titer will be determined and there will be testing for neutralizing antibodies using a validated cell-based assay.

3.1.12 12-Lead Electrocardiogram (ECG)

On dose administration days, digital 12-lead ECG measurements will be obtained at 5 minutes after the completion of the infusion. When ECGs are to be collected at the same time point as a blood collection, ECGs should be collected first. All ECGs are to be performed with the subject in a supine position having rested in this position for at least 5 minutes before each reading. ECGs are to be performed in triplicate, each at an interval of 1 to 2 minutes apart (Cohort 1) or approximately 1 minute apart (Cohort 2). See [Table 4](#) for timing window allowances with respect to performing ECG.

The following ECG parameters will be collected: PR interval, RR interval, QRS interval, and QT interval. The ECG findings will be evaluated by a qualified physician for the presence of abnormalities (qualitative assessment). The physician will assess each ECG as normal, abnormal/not clinically significant, or abnormal/clinically significant.

Normal corrected QT interval using Fridericia's formula (QTcF) is ≤ 450 msec.

Abnormalities in the ECG that appear following therapy or that result in clinical signs and symptoms are considered clinically significant for the purposes of this study and will be recorded on the AE eCRF.

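### Section 4.7.3 ties the exclusion of off-window ECG and vital-sign readings to a table without windows, and does not say which safety tables the exclusion reaches

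*SAP*

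**What the plan says.** Section 4.7.3 plans these outputs for vital signs and ECGs:

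- For vital signs: "Vital sign measurements and change from baseline will be summarized at each scheduled time point by cohort using descriptive statistics". No other vital-sign table is planned.
- For ECGs: statistics by time point on the mean of the triplicate, shift tables of the normal/abnormal category, the worst of the three interpretations at each visit, and counts of subjects in QTcF threshold (>450, >480, >500 msec) and increase (>30, >60 msec) categories over the post-baseline period.

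The section then closes with one sentence on timing: "Actual sampling times that are outside the scheduled sampling times window described in [Table 5](#) will be excluded from summary statistics".

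The two tables concerned are in Appendix A. One is titled "Table 5. Pharmacodynamic Assessments" and gives collection days for each laboratory marker. The other is titled "Table 4. Timing Window Allowances for PK/PD Sampling, ECG, and Vital Sign Measurements at Dosing Visits" and gives the tolerances in minutes. Section 3.1.12 sends the reader to Table 4 "for timing window allowances with respect to performing ECG", and Section 3.1.4 sends the reader there "for timing window allowances with respect to measurement collection".

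**The concern.** There are two faults. First, the exclusion points to a table that cannot supply what it needs. One programmer may conclude that nothing is excluded; another may apply Table 4 on the strength of the other references. The two would produce different safety tables from the same data.

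Second, the sentence stands at the end of the section, after all the outputs listed above, and is not limited to any of them. Vital signs and ECGs are named components of the primary safety endpoint in Section 2.1. An extreme reading taken off schedule is as relevant to safety as one taken on time. It should not depend on a programmer's reading of the term summary statistics whether that value enters a count of subjects above a QTcF threshold. For vital signs there is no count or worst-grade table that could hold such a value.

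**Working it through.** The plan gives no figure on this point, so there is none to reproduce. The check compares the sections and then gauges how narrow the windows are.

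**1. Which table holds the windows.**

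| Place in SAP | Subject | Table cited for windows |
|---|---|---|
| Section 3.1 | PK/PD, ECG, vital signs | Table 4 |
| Section 3.1.4 | Vital signs | Table 4 |
| Section 3.1.12 | ECG | Table 4 |
| Section 4.9.1 | PK concentrations | Table 4 |
| Section 4.7.3 | ECG, vital signs | Table 5 |

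Table 5 contains immunoglobulins, immune complexes, albumin, anti-Dsg titers and the exploratory markers, each with a list of study days. It has no tolerance column and no ECG or vital-sign row. Section 4.7.3 is the one that is out of line.

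**2. How the parallel rule is worded.** Section 4.9.1 also excludes off-window samples, but it names the output affected (summaries of PK concentrations) and the use that is kept (calculation of PK parameters). Section 4.7.3 does neither.

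**3. What backstop tables exist.** Section 4.7.2 gives laboratory tests an incidence of abnormalities and a worst on-study grade. Section 3.1.4 has vital-sign abnormalities graded by CTCAE, but Section 4.7.3 never tabulates those grades.

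**4. How much time the Table 4 vital-sign windows cover.** Inputs: ±5 minutes at "15, 30, and 45 minutes after start of infusion"; ±10 minutes at completion; ±10 minutes at "30 minutes, 1 and 2 hours post end-of-infusion"; infusion of 60 ± 15 minutes (Section 3.1.14). Time runs from infusion start to 2 hours after its end, and overlapping windows are counted once.

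- 60-minute infusion: windows 10–20, 25–35, 40–50, 50–70, 80–100, 110–130 and 170–180. Covered: 10 + 10 + 10 + 20 + 20 + 20 + 10 = 100 of 180 minutes. Uncovered: 80/180 = 44%. Within the infusion itself, 0–10, 20–25 and 35–40 are uncovered: 20/60 = 33%.
- 45-minute infusion: windows 10–20, 25–55 (three merged), 65–85, 95–115 and 155–165. Covered: 10 + 30 + 20 + 20 + 10 = 90 of 165. Uncovered: 75/165 = 45%.
- 75-minute infusion: windows 10–20, 25–35, 40–50, 65–85, 95–115, 125–145 and 185–195. Covered: 10 + 10 + 10 + 20 + 20 + 20 + 10 = 100 of 195. Uncovered: 95/195 = 49%.

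These are shares of clock time. They show only that a reading taken at an unplanned moment can easily miss every window.

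**5. Repeat readings.** Section 3.1.4 requires an abnormal vital sign to be repeated after 5 minutes of rest. If the first reading is on time at 15 minutes, the repeat comes at 20 minutes or later, at or past the edge of the ±5-minute window. The plan does not say how repeats enter the tables.

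**6. ECGs.** The Table 4 window is 5 ± 10 minutes after the end of infusion, which is 20 minutes wide. By Tables 2 and 3, ECGs fall on dosing days only on Days 0 and 28 in Cohort 1 and Days 0, 14 and 28 in Cohort 2. One excluded ECG is therefore one of two, or one of three, post-infusion ECGs for that subject.

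**The case against.** The case against a serious reading of this point is good in several respects.

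- **A reader might infer that off-window readings disappear from the primary safety endpoint. They do not.** Sections 4 and 4.1 list all captured data. Section 3.1.12 sends ECG abnormalities that appear after therapy to the AE form, and Section 4.7.1 tabulates them as TEAEs. For vital signs the safeguard is weaker: the SAP grades abnormalities but has no equally explicit sentence sending them to the AE form.
- **The exclusion may not reach the QTcF counts.** Section 4.7.3 uses the term summary statistics for the by-time-point ECG values and describes the shift tables and QTcF categories as numbers and percentages of subjects. On that reading the exclusion is already as narrow as it should be. This is plausible, but the text does not settle it.
- **A reader might infer that a slowed infusion pushes readings out of window.** Table 4 anchors the ECG and the later vital signs to the end of infusion, and the 15-, 30- and 45-minute readings to its start, so slowing alone displaces neither. A reading prompted by a reaction would be an extra one, and the vital-sign table, which covers scheduled time points only, would omit it even without this rule. That excluded readings would tend to be the abnormal ones is an inference; the SAP does not say so.
- **A reader might put the loss at one subject in 8 (12.5%) or one in 12 (8.3%) becoming 0%.** That requires an incidence table governed by the rule. None is planned for vital signs, and for QTcF it is uncertain.
- **A reader might also fault the use of Day 0 as baseline at every dosing visit.** The SAP uses that baseline consistently for safety, and each visit's pre-infusion reading is itself a scheduled time point. Change from the same-day value is an optional addition, not a correction.

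What stands is the wrong table, the unstated reach of the rule, and the absence of any vital-sign table that could hold an off-schedule extreme.

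**Conclusion.** The point holds as a should-fix. The table reference is wrong on the face of the document, and the intended table is clear from four other places in the SAP. Beyond that, the exclusion lacks the explicit limit that the PK rule has, so its effect on the QTcF categories, the ECG shift tables and the worst ECG interpretation is undetermined. For vital signs, an off-schedule or repeat extreme could be absent from every planned vital-sign table while remaining in the listings and, if reported as an AE, in the TEAE tables.

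The number of readings that would be lost cannot be derived from the document. The uncovered share of 44% to 49% of clock time assumes infusions of 45 to 75 minutes and readings kept or dropped by the Table 4 windows alone. It indicates that correcting the table number would still leave off-schedule readings open to exclusion. The safety analysis is descriptive, so no test or error rate is affected.

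**What to change.** In Section 4.7.3:

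1. Replace Table 5 with Table 4, and note that Table 4 sets minute windows for dosing visits only.
2. Limit the exclusion to descriptive statistics by time point, and say that it does not apply to the ECG shift tables.
3. State that all post-baseline readings, including off-window, repeat and unscheduled ones, count in the QTcF threshold and increase categories and in the worst ECG interpretation.
4. Add a summary of the worst post-baseline CTCAE grade for vital signs on the same basis, parallel to the laboratory summary in Section 4.7.2.

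The cost is a few sentences of SAP text and minor programming. No new data are needed. The change should be made before database lock, when Section 6 has the programming specifications finalized.
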